2.4.6.2 Concentration/parasitemia analyses

The evaluation of the relationship between parasitemia (blood film) and concentration of OZ439/FQ may be performed in a separate analysis pooling data from different studies.

The evaluation of the relationship between parasitemia (measured by qPCR) and concentration of OZ439/FQ may be performed in a separate analysis pooling data from different studies.

These analyses if performed will be described in ad-hoc separate plans and will be reported in separate reports.

2.4.6.3 Concentration/ECG analyses

All the analyses will be performed on the PK/PD Safety population.

Endpoints

The Concentration-ECG analyses will be based on 12-lead ECG method.

The ECG parameters will include heart rate, QTcB, QTcF, PR and QRS intervals, corresponding to the change from baseline value. All post-dose assessments on Visit 2 (Day 0 hour 2, 4, 6, 8 and 12), Visit 3 (Day 1 hour 24), and Visit 4 (Day 2 hour 48) will be included, except Visit 5 (Day 3 hour 72), Visit 6 (Day 4 hour 96) and Visit 9 (Day 7 hour 168).

The pharmacokinetic endpoint will be the PK concentration of SSR97193, its active metabolite SSR97213 and OZ439 compounds. Post-dose concentrations below the lower limit of quantification (LLOQ) will be imputed to LLOQ / 2. LLOQ is defined as 5 ng/mL for FQ and SSR97213, 1 ng/mL for OZ439.

Relationships between concentrations (FQ, SSR97213 and OZ439) and change from baseline in ECG parameters will be analyzed into two ways:

- by combining the two compounds FQ and SSR97213 using the molecular weight (MW) 433.77 g.mol-1 for ferroquine and 419.74 g.mol-1 for SSR97213, in order to obtain an “total” concentration, separately from OZ439 (molecular weight of 469.28 g.mol-1)
- by using ferroquine, SSR97213 blood drug concentrations and OZ439 plasma concentrations as covariates in the same model

The relationship will be explored using data from OZ439/FQ on the restricted time window [Day 0, hour 2 – Day 2 hour 48]. Prediction of changes in ECG parameters (with 90% CI) will be obtained for each compound entering the models at each dose $C_{max,}$.

Exploratory plots

The relationship between change from baseline in ECG parameters and FQ (respectively SSR97213, OZ439) concentrations will be first explored graphically, in order to investigate any

potential delayed or sustained effects and the type of modeling to be done, using the following plots, by treatment group:

- Plot of mean (\pm SEM) change from baseline in ECG data and mean FQ (respectively SSR97213, OZ439) concentration versus time (hours post-dose) overlaid onto the same plot
- Hysteresis plot of mean change from baseline in ECG data and mean FQ (respectively SSR97213, OZ439) concentrations
- Histogram of distribution of time of largest change from baseline in HR, PR, QRS, QTcB and QTcF and largest FQ (respectively SSR97213 and OZ439) concentrations, respectively;
- Histogram of distribution of time of smallest change from baseline in HR, PR, QRS, QTcB and QTcF and largest FQ (respectively SSR97213, their total concentrations and OZ439) concentrations, respectively.

Linear modeling

The linear direct (or indirect depending on the hysteresis plots) model will be carried out for the relationship between concentrations and change from baseline in ECG parameters, with fixed terms for population intercept, and nominal time intercept, with the concentration (slope), and with random terms for individual patient deviation from the population intercept and slope, and using an unstructured variance-covariance structure for random coefficients and a common variance for error, using SAS Proc Mixed®. The analysis model will be the following:

For the model with ferroquine and SSR97213 total concentration using MW:

Change from baseline = $(\alpha + A_i) + (\beta + B_i) \times \text{Concentration}_{ij} + \text{error}$, with $i = \text{patient}$ and $j = \text{time}$

For the model where ferroquine and SSR97213 blood drug concentrations will be used as covariates simultaneously:

Change from baseline = $(\alpha + A_i) + (\beta_1 + B_{1i}) \times \text{Ferroquine Concentration}_{ij} + (\beta_2 + B_{2i}) \times \text{SSR97213 Concentration}_{ij} + \text{error}$, with $i = \text{patient}$ and $j = \text{time}$

with:

- α and β are the fixed population intercept and concentration slope.
- A_i and B_i are the random intercept and concentration slope for the i^{th} patient, with A_i and B_i assumed to be normally distributed with null mean and an unstructured variance-covariance matrix per subject block.

- Concentration_{ij} is the concentration for the ith patient at the jth time point

When OZ439 is added to the model, a term $(\beta_3 + B_{3i}) \times OZ439$ Concentration_{ij} will be added to the model, OZ439 concentrations being used unchanged or converted to $\mu\text{mol/L}$ depending on the model used.

The influence of time (as factor) could be investigated as covariate if relevant and if it allows to improve the model.

Estimates and 90% CIs of coefficients of the linear regression model, and the prediction (estimate and 90% CI) in change from baseline of ECG parameters corresponding to the Cmax value (geometric mean) for each FQ dose group will be provided for FQ and SSR97213 respectively, and will be calculated as follows:

- For the models with ferroquine and SSR97213 total concentration using MW:
 - Estimated change from baseline at total concentration Cmax = $\beta_{\text{estimated}} \times \text{total concentration Cmax geometric mean (GM)}$
- For the models with ferroquine and SSR97213 concentrations as covariates:
 - Estimated change from baseline at ferroquine Cmax = $\beta_1 \text{ estimated} \times \text{ferroquine Cmax GM} + \beta_2 \text{ estimated} \times (\text{mean of SSR97213 concentrations obtained at individual ferroquine tmax})$
 - Estimated change from baseline at SSR97213 Cmax = $\beta_1 \text{ estimated} \times (\text{mean of ferroquine concentrations obtained at individual SSR97213 tmax}) + \beta_2 \text{ estimated} \times \text{SSR97213 Cmax GM}$
- For the models including OZ439, contribution of OZ439 will be addressed in the same way, that is, by estimating the change from baseline at OZ439 Cmax GM conditioned to mean concentrations for ferroquine, SSR97213 or the total of their concentrations obtained at OZ439 tmax, or by conditioning predictions for ferroquine, SSR97213 or the total of their concentrations by the mean of OZ439 concentrations obtained at the tmax of interest.

Scatter plots of change from baseline versus FQ, SSR97213 and OZ439 concentrations, respectively, with the regression line overlaid, will also be provided.

Goodness-of-fit and residual plots will be provided. In case of lack of fit (ie, the linear model is not adequate), alternative models like non-linear models (exponential, E_{max}) and/or Model Averaging (MA, [4]) might be explored.

Model Averaging to Concentration-QT analysis

Model averaging will be used in case it is not possible to determine the best model among competing models (linear, exponential and Emax), Model averaging (MA) will provide estimators

which will have good robustness properties compared to the linear model or non-linear model estimates.

The estimated endpoint will be the drug effect on delta QTcF at the C_{max} values (geometric means) observed concentrations at the maximal dose (FQ 400 mg/OZ439 1000 mg).

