2.1.5.5 ECG variables

A 12-lead ECG recording on Visit 2 (Day 0 hour 0, 2, 4, 6, 8, 12), Visit 3 (Day 1 hour 24), Visit 4 (Day 2 hour 48), Visit 5 (Day 3 hour 72) only if patient still hospitalized, Visit 6 (Day 4 hour 96) only if patient still hospitalized and Visit 9 (Day 7 hour 96), using a 12-lead ECG to extract triplicate measurements at each theoretical time point (each replicate record will be centrally read by a Core Lab Banook group (semi-automatic reading). The parameters that will be received from the ECG reading center are: RR, QT, QTcF, QTcB, PR and QRS (msec) and heart rate (bpm), but also ST deviation, T-wave morphology, U wave presence or absence.

All ECGs (triplicate) will be manually read by independent experts (except Visit 1 (Screen) for which automatic reading will be done).

For all quantitative ECG parameters, the mean of triplicate ECGs at each time point will be used for all analyses including PCSA analyses. As far as at least one record is available from a triplicate, it will be used in the mean calculations for analyses. No time restriction is applied for calculation of mean values from triplicate ECGs performed at the same visit.

For each set of triplicate ECGs, the associated date and time of the assessment is taken as the date and time of the first record of the triplicate.

The value to be used as baseline will be defined as the average of the triplicate assessments done on Day 0 T0 or the last available time point prior to first dosing for each treatment group.

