2.3.5.2 PK/PD safety population

Pharmacokinetic/pharmacodynamic (PK/PD safety) population: all patients included in the PK population and having at least the baseline and one post-baseline ECG assessment.

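### The concentration-ECG models omit baseline as a covariate, so the OZ439 slope is valid but less precise than it could be and moves with chance baseline imbalance

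*SAP*

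**What the plan says.** The response is defined in SAP 2.4.6.3: "The ECG parameters will include heart rate, QTcB, QTcF, PR and QRS intervals, corresponding to the change from baseline value". The model is described in words as one "with fixed terms for population intercept, and nominal time intercept, with the concentration (slope), and with random terms for individual patient deviation".

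The displayed equations are narrower. They hold an intercept, one or more concentration slopes, the matching random terms and error, and the definitions beneath them say that alpha and beta "are the fixed population intercept and concentration slope". OZ439 enters through one further slope term. Time appears in the verbal description but not in the equations, and is then made optional: "The influence of time (as factor) could be investigated as covariate if relevant and if it allows to improve the model". Baseline is not named as a term or as a candidate covariate anywhere in the section.

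A baseline ECG exists for everyone analysed, because SAP 2.3.5.2 defines the PK/PD safety population as "all patients included in the PK population and having at least the baseline and one post-baseline ECG assessment". SAP 2.1.5.5 states: "The value to be used as baseline will be defined as the average of the triplicate assessments done on Day 0 T0". It then allows the last available pre-dose time point as a fallback, and a mean may rest on a single record of the triplicate.

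On output, "Prediction of changes in ECG parameters (with 90% CI) will be obtained for each compound entering the models". In the linear models these predictions are estimated slopes multiplied by concentrations (the geometric mean Cmax of the compound in question), with no intercept. The data come from a limited period: "The relationship will be explored using data from OZ439/FQ on the restricted time window", from 2 to 48 hours after dosing.

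**The concern.** A patient's baseline deviates from that patient's usual level, and the deviation is subtracted from every post-dose value. Change is therefore negatively related to baseline, and taking the difference does not remove that relation.

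OZ439 exposure is set largely by randomised arm (0, 300, 600 or 1000 mg), so part of the OZ439 slope is a comparison between patients. If the 1000 mg arm happens to start with a higher mean QTcF, its mean change tends to be lower and the slope is pulled down; a lower start does the opposite. Because the SAP prediction is built from the slope, this error passes into the reported QTcF effect at Cmax.

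Protocol 3.3 names QTcF prolongation as an identified risk of both components, and SAP 2.4.6.3 makes the effect on delta QTcF at the maximal dose the target of its model-averaging step. It is worth making that number less dependent on the luck of the baseline draw when the data to do so are already collected.

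**Working it through.** **1. The plan's own figure.** The documents give no SD, precision or sample size for the concentration-ECG analysis. The only figure that feeds in is the number of patients. Protocol 10.1 gives 30 evaluable per arm and about 15% dropout: 30 / (1 - 0.15) = 35.3, consistent with its approximately 35 per arm and 140 in total.

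**2. Assumptions, none from the documents.** Total QTcF SD 17 ms; correlation ρ between baseline and post-dose QTcF of 0.5 to 0.9; random-slope SD 5 ms; between-patient spread of exposure 0.5 on the log scale; an OZ439 profile that is either fast-falling or sustained over 48 h; arm A at concentration 0. OZ439 is not sampled in arm A, and the SAP does not say how that arm enters the model.

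**3. Mechanism.** With equal variances, the regression of change on baseline has coefficient ρ - 1, that is -0.5 at ρ = 0.5 and -0.1 at ρ = 0.9. The difference in mean baseline between two arms of 30 has SD 17 × √(2/30) = 4.4 ms.

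**4. Precision.** I simulated trials with 30 patients per arm, the seven ECG times (2, 4, 6, 8, 12, 24 and 48 h), a random intercept and random OZ439 slope, and no true drug effect. Each was fitted by generalised least squares at the true variance components, with 250 trials per scenario and FQ terms left out. The slope is in ms per typical 1000 mg Cmax, so its SE is also the SE of the OZ439 contribution to the prediction there. With time as a factor:

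| ρ | OZ439 profile | SE without baseline | SE with baseline | SE (CI width) cut | Variance cut |
|---|---|---|---|---|---|
| 0.5 | fast-falling | 2.37 | 2.20 | 7.2% | 13.8% |
| 0.5 | sustained | 2.65 | 2.19 | 17.4% | 31.7% |
| 0.7 | fast-falling | 1.95 | 1.89 | 3.1% | 6.1% |
| 0.7 | sustained | 2.19 | 1.99 | 9.1% | 17.4% |
| 0.8 | fast-falling | 1.70 | 1.67 | 1.8% | 3.5% |
| 0.8 | sustained | 1.88 | 1.78 | 5.3% | 10.4% |
| 0.9 | fast-falling | 1.36 | 1.35 | 0.7% | 1.5% |
| 0.9 | sustained | 1.49 | 1.46 | 2.0% | 4.0% |

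Over all scenarios, including those without the time factor, the variance ratio (unadjusted / adjusted) ran from 1.005 to 1.475. Excluding arm A (ρ = 0.7, sustained) gave SE 2.77 without and 2.54 with baseline, a cut of 8.3%, so the direction does not depend on how arm A is handled.

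**5. Dependence on imbalance.** Without baseline, each 1 ms of imbalance between the 1000 mg arm and the lowest arm moved the slope by -0.02 to -0.27 ms. For a one-SD imbalance this is 0.02 × 4.4 = 0.1 ms to 0.27 × 4.4 = 1.2 ms in the predicted effect at the 1000 mg Cmax. With baseline in the model the dependence was within simulation noise of zero. For scale, at ρ = 0.7 with a sustained profile the shift is 0.159 × 4.4 = 0.7 ms, against an unadjusted 90% half-width of 1.645 × 2.19 = 3.6 ms.

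**6. Validity of the planned estimate.** The unadjusted slope showed no bias beyond simulation noise. Its 90% CI covered 86 to 92% across scenarios; with 250 trials the simulation SE is √(0.9 × 0.1 / 250) = 1.9 percentage points, so this is compatible with 90%.

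**7. Fewer usable times.** Protocol Table 3 schedules no FQ sample at 2 or 48 h and no OZ439 sample at 8 h, so ECG, FQ and OZ439 coincide only at 4, 6, 12 and 24 h. A second simulation used those four times, 35 per arm, FQ and time terms, between-patient SD 12 to 20 ms, within-patient SD 8 to 12 ms and random-slope SD 0 or 5. It gave a variance cut of 2 to 28% and a shift of -0.05 to -0.27 ms per 1 ms of imbalance, or roughly 0.2 to 1.0 ms for a one-SD imbalance.

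**The case against.** The strongest reply is that the planned model is a valid analysis. A reader might infer from the word imbalance that the slope is biased or its CI too narrow. The documents do not support that: allocation is randomised, the imbalance is chance, and the check found no bias and about nominal coverage. This part of the objection stands in full.

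A reader might also take the shift in the raw difference in mean change between two arms as the size of the problem. Across plausible variances that is about 0.7 to 1.8 ms for a one-SD imbalance. SAP 2.4.6.3 does not report that difference. It reports slope-based predictions, and much of the slope information is within patients, where a baseline term changes nothing. The relevant figure is the smaller 0.1 to 1.2 ms.

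Nor do the documents promise a full Day 0 triplicate for everyone. SAP 2.1.5.5 allows an earlier pre-dose time point and fewer records. A baseline value still exists for each analysed patient, which is all that the covariate needs.

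Finally, the stakes are limited. The QTc-concentration objective is exploratory (Protocol Table 1, SAP 1.2.3), no decision threshold is attached to the estimate, and QT safety is also covered by the adverse events of special interest in Protocol 9.2 and the summaries and listings in SAP 2.4.5.5. That sets the weight of the point but gives no reason to leave the covariate out.

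**Conclusion.** The omission is plain in the text, and adding baseline is a nearly costless improvement. The planned estimator is sound. What is lost is some precision, plus independence from the observed baseline imbalance.

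The gain is a variance cut of roughly 1 to 30%, equivalent to a CI narrower by under 1% to about 17%, and removal of a shift of about 0.1 to 1.2 ms per one-SD imbalance. The upper ends need a low correlation (ρ = 0.5) or sustained exposure. At ρ of 0.7 or more with fast-falling exposure the CI gain is about 3% or less. All of this rests on assumed QTcF variability, on arm A entering at concentration 0, and on simulations that treat the variance components as known. The direction was the same in every scenario. The primary ACPR analysis and the sample size are not affected.

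**What to change.** In SAP 2.4.6.3, add the baseline value of the same ECG parameter, centred at the overall mean, as a fixed covariate in every concentration-ECG model, including the non-linear and model-averaged versions. Specify it before database lock so that adjustment is not a post hoc choice.

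The slope-times-Cmax prediction formulas need no change, because the intercept and a centred baseline term do not enter them. Any prediction that includes the intercept should be made at mean baseline.

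The cost is one degree of freedom and one line of SAP text, with no new data. The same edit could settle two loose ends in the section: whether nominal time is a fixed term or optional, and how arm A enters the OZ439 models.

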2.4.6.4 Analyses of quality of life/health economics variables

Not applicable

2.5 DATA HANDLING CONVENTIONS

2.5.1 General conventions

The following formulas will be used for computation of parameters.

Demographic formulas

- Body mass index (kg/m^2) = (Weight in kg)/ (Height in meters)²
- Time from first diagnosis of current malaria infection: day of randomization - day of diagnosis of current malaria infection
- Prior/concomitant/follow-up medications:

Only the date of medication start/end will be reported in the eCRF (no time), then by convention medication taken the day of randomization will be classified as concomitant.

Renal function formulas

Creatinine clearance value is derived using the equation of Cockroft and Gault: CrCl is calculated using weight assessed at the same visit than creatinine was assessed.

For patients > 18 years old:

$CrCl (mL/min) = F \times (140 - \text{age(years)}) \times \text{weight(kg)} / [\text{serum creatinine } (\mu\text{mol/L})]$ where F = 1.23 if male, and 1.04 if female

For patients ≤ 18 years old (Bedside Schwartz Formula):

$eGFR (\text{mL/min}/1.73 \text{ m}^2) = (0.413 \times \text{Height in cm}) / [\text{serum creatinine } (\mu\text{mol/L})]$

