Appendix 2 Clinical laboratory tests

- The tests detailed in Table 11 will be performed by the local laboratory
- Protocol-specific requirements for inclusion or exclusion of participants are detailed in Section 6.1 and Section 6.2 of the protocol.
- Additional tests may be performed at any time during the study as determined necessary by the investigator or required by local regulations.

Table 11 - Protocol-required safety laboratory assessments

Laboratory assessments		Parameters			
Hematology	Platelet count		WBC Count with Differential:		
	RBC count		Neutroph	nils	
	Hemoglobin		Lymphod	cytes	
	Hematocrit		Monocytes Eosinophils		
	Reticulocytes ^a				
			Basophils		
Clinical chemistry ^b	Urea	Potassium	Aspartate aminotransferase (AST)	Total bilirubin	
	Lactate dehydrogenase ^a	Sodium	Alanine aminotransferase (ALT)	Direct bilirubin if total bilirubin ≥ULN ^a	
	Creatinine	Magnesium (screening)	Alkaline phosphatase	Albumin	
	Creatinine clearance ^C	Calcium (screening)		Haptoglobin ^a	
	Creatine kinase				
	Glucose (non-fasting)				
Routine urinalysis	Specific gravity				
	pH, glucose, protein, blood, ketones, bilirubin, leukocyte esterase by dipstick				
	Microscopic examination (if blood or protein is abnormal)				
	 Pregnancy test (urine β-HCG)^d for WOCBP 				
Other screening tests	Hepatitis serology: HAV IgM, HBsAg, HCV Ab, and/or HCV RNA (if known)				
	 The results of each test must be entered into the e 				

NOTES:

- a Test not needed for screening but must be available during the study to monitor the participant's health status. The test must be either available locally or in a national reference laboratory with which the site has an agreement for performing the test.
- b Details of liver chemistry criteria and required actions and follow-up assessments are given in Section 9.2 and Appendix 7. .
- c For participants >18 years old, the creatinine clearance (CrCl) will be calculated from Cockroft and Gault formula: CrCl (mL/min) = 1.23 (for male) or 1.04 (for female) x weight (kg) x (140 Age) / serum creatinine (μmol/L) with age in years. For participants ≤18 years old, the GFR Bedside Schwartz Formula should be used: eGFR (mL/min/1.73 m²) = 0.413 x height (cm) / serum creatinine (mg/dL)
- d Local urine testing will be standard for the protocol unless serum testing is required by local regulation or IRB/IEC.

Investigators must document their review of each laboratory safety report.

Property of the Sanofi group - strictly confidential

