1.6 STATISTICAL MODIFICATIONS MADE IN THE STATISTICAL ANALYSIS PLAN

The primary efficacy population will be the PK/PD population instead of the mITT population stated in the protocol.

A per-protocol [PP] population was added in order to align the analysis population with the primary endpoint of the study. All populations have been further clarified from the protocol definitions

The derivation of the secondary endpoint, Fever clearance time (FCT), has been added. FCT will be assessed by measuring the time from the first dose until the first time that the body temperature dropped and remained <37.5 °C.

Time to 50% parasite reduction (T_{PC50}) will also be calculated in addition to the time to 99% PR.

The evaluation of the relationship between parasitemia (as measured on thick blood film and/or by qPCR) and concentration of OZ439/FQ may be performed in a separate analysis pooling data from different studies and be reported in a separate report.

The terminal half-life ($t_{1/2}$) for OZ439 and ferroquine will not be estimated as this endpoint does not contribute to the objectives of the study.

The definition of baseline to be used for efficacy analyses has been clarified.

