2.1.5.3 Laboratory safety variables

Clinical laboratory data consists of blood analysis, including hematology, clinical chemistry, and urinalysis. Local clinical laboratory values after conversion will be analyzed into standard international units and international units will be used in all listings and tables.

Blood samples for clinical laboratories will be done locally at Visit 1 (Screening/pre-dose), Visit 4 (Day 2 hour 48), Visit 5 (Day 3 hour 72) only if patient still hospitalized, Visit 6 (Day 3 hour 96) only if patient still hospitalized, Visit 9 (Day 7 hour 168), Visit 11 (Day 14), Visit 12 (Day 21) and Visit 13 (Day 28) unless otherwise specified. The laboratory parameters will be classified as follows:

- Hematology
 - **Red blood cells and platelets and coagulation:** hemoglobin, hematocrit, reticulocytes (not needed at screening), haptoglobin (not needed at screening), red blood cell count, platelet count.
 - **White blood cells:** white blood cell count, neutrophils, lymphocytes, monocytes, basophils, eosinophils
- Clinical chemistry
 - **Metabolism:** glucose, albumin, creatine phosphokinase
 - **Electrolytes:** sodium, potassium, calcium, magnesium
 - **Renal function:** creatinine, creatinine clearance, urea
 - **Liver function:** alanine aminotransferase (ALT), aspartate aminotransferase (AST), alkaline phosphatase (ALP), lactate dehydrogenase, total bilirubin (TBIL) and direct bilirubin (BILDIR, not needed at screening)
 - **Pregnancy test (screen):** Serum or urine β -human chorionic gonadotropin (all female patients)
 - **Viral hepatitis serology (screen):** HAV IgM, HBsAg, HCV Ab, and/or HCV RNA

Urine samples will be collected as follows:

- **Urinalysis** - quantitative analyses: pH, specific gravity, proteins, glucose, blood, ketones, bilirubin, leukocyte esterase by dipstick. Microscopic examination (if blood or protein is abnormal)

Creatinine clearance is calculated locally according to formulae specified in the protocol:

- Cockroft and Gault formula for patients more than 18 y.o.
- GFR Bedside Schwartz formula for patients between 14 y.o and <18 y.o.

Technical formulas are described in Section 2.5.1.

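### SAP 2.5.1 pairs the Bedside Schwartz constant 0.413 with creatinine in µmol/L instead of mg/dL; if programmed, eGFR at age 18 or under comes out about 88 times too low

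*SAP*

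**What the plan says.** - **SAP 2.5.1, renal function formulas.** The section opens with "The following formulas will be used for computation of parameters". For age 18 or under it gives "0.413 \times \text{Height in cm}) / [\text{serum creatinine } (\mu\text{mol/L", with the result in mL/min/1.73 m².
- **Protocol Appendix 2, Table 11 note c.** For the same age group and the same result unit it gives "0.413 x height (cm) / serum creatinine (mg/dL".
- **Adult line.** Cockcroft-Gault has the same constants (1.23 for men, 1.04 for women) and the same creatinine unit (µmol/L) in both documents. Only the line for the younger group differs.
- **SAP 1.6.** The list under "STATISTICAL MODIFICATIONS MADE IN THE STATISTICAL ANALYSIS PLAN" does not mention the renal formula.
- **Where clearance is computed.** SAP 2.1.5.3 says "Creatinine clearance is calculated locally according to formulae specified in the protocol", and Protocol Appendix 2 says of the table that includes clearance: "The tests detailed in Table 11 will be performed by the local laboratory". SAP 2.1.5.3 then adds "Technical formulas are described in Section 2.5.1".
- **Age cut.** SAP 2.1.5.3 has "GFR Bedside Schwartz formula for patients between 14 y.o and <18 y.o" and gives Cockcroft-Gault to those older than 18. Protocol Appendix 2 and SAP 2.5.1 both cut at ≤18 / >18.
- **Limits applied to the result.** For values from the Bedside Schwartz formula, SAP Appendix B sets a low-clearance flag (a potentially clinically significant abnormality, PCSA) below 60 mL/min/1.73 m² and quotes a normal range of 80 to 120 after age 12.

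**The concern.** A constant of 0.413 cannot be right for both mg/dL and µmol/L, because the two units differ by a factor of nearly 90. Nothing suggests that a different formula was intended: the age group, the height unit, the result unit and the constant are all unchanged.

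The error has a plausible route into the tables. SAP 2.1.5.3 and 2.4.5.3 put laboratory data into SI units for analysis, so the programmer will hold creatinine in µmol/L and can apply 2.5.1 exactly as printed.

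The trial enrols from age 14, so ages 14 to 18 are exposed to this line. A clearance table in which all of them are abnormal from the start would carry no safety information on renal function. SAP 2.4.5.3 also provides for PCSA incidence by baseline status. In that display everyone in this group with a baseline value would sit in the abnormal stratum, and the flag could not show a new decline.

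**Working it through.** **Inputs from the documents:** the constant 0.413 and both creatinine units (Protocol Appendix 2 note c; SAP 2.5.1); the <60 limit, the 80-120 range, and the high-creatinine flag above 132 µmol/L at 12 to 16/18 years (SAP Appendix B).

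**Assumptions, not in the documents:** creatinine molar mass 113.12 g/mol, so 1 mg/dL = 10 mg/L ÷ 113.12 g/mol = 88.4 µmol/L (range 88.3 to 88.5). The heights and creatinine values below are illustrative.

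**1. One patient, 160 cm, creatinine 60 µmol/L.**
- Protocol: 60/88.4 = 0.679 mg/dL; 0.413 × 160 × 88.4 / 60 = 97.4 mL/min/1.73 m² (97.2 to 97.5 over the conversion range).
- SAP 2.5.1: 0.413 × 160 / 60 = 1.10.
- Ratio: 88.4. It is the same at every height and creatinine value, because it is only the unit conversion.

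**2. A wide grid, 140-190 cm and 30-150 µmol/L.**

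| | Lowest | Highest |
|---|---|---|
| SAP 2.5.1 | 0.413 × 140 / 150 = 0.39 | 0.413 × 190 / 30 = 2.62 |
| Protocol | 0.413 × 140 × 88.4 / 150 = 34.1 | 0.413 × 190 × 88.4 / 30 = 231.2 |

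Every SAP value is far below 60.

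**3. Creatinine needed to reach 60, and so escape the flag.**
- SAP 2.5.1: 0.413 × 140 / 60 = 0.96 µmol/L, up to 0.413 × 190 / 60 = 1.31 µmol/L.
- Protocol: 85.2 µmol/L at 140 cm, 97.4 at 160 cm, 115.6 at 190 cm.

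**4. Check against the SAP's own range.** At 160 cm, a result of 80 to 120 under SAP 2.5.1 needs creatinine between 0.413 × 160 / 120 = 0.55 and 0.413 × 160 / 80 = 0.83 µmol/L. This step does not use the conversion factor. Appendix B treats creatinine as high only above 132 µmol/L at these ages, so the printed formula and the printed limits cannot belong together. Multiplying by 88.4 for the protocol unit gives about 49 to 73 µmol/L, which does fit.

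**5. Change from baseline.** At 160 cm, creatinine rising from 60 to 90 µmol/L:
- Protocol: 97.36 to 64.91, a fall of 32.45.
- SAP 2.5.1: 1.10 to 0.73, a fall of 0.37.

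**6. Constant that would suit µmol/L.** 0.413 × 88.4 = 36.5.

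**The case against.** **The error may never reach the tables.** SAP 2.1.5.3 says that clearance is computed at the sites with the protocol formulae, and those carry the consistent unit. The absence of an entry in SAP 1.6 fits a slip better than an intended change. This stands as far as it goes: a reader might infer that the clearance tables will be wrong, and the documents do not support that. Nor do they exclude it. The same section sends the reader to 2.5.1, which describes clearance as derived and its formulas as the ones to be used.

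**It would be noticed, and little depends on it.** Values of 0.4 to 2.6 in every adolescent are implausible and would probably be caught at output review. The displays are descriptive, and the separate creatinine flag still works. This is a fair argument for a low grade, but not for leaving a wrong formula in the plan.

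**Two stronger readings do not hold.**
- A reader might infer that 16- to 18-year-olds could be judged against the adult clearance grades and called end-stage. Appendix B ties the adult grades by footnote to MDRD or Cockcroft-Gault, and the children's limits to Bedside Schwartz. Its children's row from 2 years has no upper age. A Schwartz value therefore belongs with the <60 limit.
- A reader might infer that the rule in 2.5.1 requiring weight from the same visit cannot be met on Days 7, 14 and 21, because the weight row of the Schedule of Activities shows only screening, hospital discharge and Day 28. But Protocol 9.4.1 has weight recorded with the physical examination, which is scheduled at 168 h, and SAP 2.1.5.4 counts weight among the vital signs, which are taken on all three days. The documents are inconsistent about when weight is taken; they do not show the rule to be impossible.

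**Conclusion.** The formula in SAP 2.5.1 is wrong as written. It conflicts with Protocol Appendix 2 and with the limits in SAP Appendix B, and it understates eGFR by a constant factor of about 88. That figure rests only on the assumed conversion of 88.4 µmol/L per mg/dL; the conflict with Appendix B does not need it.

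The consequence is conditional on 2.5.1 being programmed. In that case the low-clearance flag is raised at baseline and at every visit for every participant aged 14 to 18 with a realistic creatinine value, and the values and changes from baseline for this group are uninformative. If the locally calculated clearance is analysed, nothing in the tables changes.

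Either way the effect is confined to descriptive clearance summaries and PCSA counts, through the values of an age group whose size the documents do not give. The separate creatinine flag and the efficacy analyses are untouched. This is a minor correction. The missing formula for age exactly 18 in SAP 2.1.5.3 is a wording slip, since both formula passages agree on ≤18 / >18.

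**What to change.** - In SAP 2.5.1, give creatinine in mg/dL in the Bedside Schwartz line, as in Protocol Appendix 2. If µmol/L is kept, write 36.5 x height in cm / creatinine in µmol/L.
- State in SAP 2.1.5.3 or 2.5.1 whether the locally calculated or the derived clearance is analysed.
- Align the age wording in SAP 2.1.5.3 with ≤18 / >18.
- Optional: reconcile the same-visit weight rule in 2.5.1 with the weight row of the Schedule of Activities, Protocol 9.4.1 and SAP 2.1.5.4.

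The cost is a few lines of SAP text. No new data are needed, and no other analysis changes.
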